5.5 Rationale for choice of doses

Given that in a study using a different fish oil source and formulation we found that 1 g of essential fatty acids gave a mild but significant increase in plasma SPM levels (25) we chose the lowest dose in the study to be of 1.5g. We then chose to investigate two other doses that were within the **European Food Safety Authority's Tolerable Upper Intake Level for supplements containing both EPA and DHA (See Appendix 2 and 3)**. Given that this limit is of 5 g and previous study with both healthy volunteers and patients demonstrated that doses up to 4 g are well tolerated (22-24), we chose the remaining 2 doses to be 3.0 g and 4.5 g. In addition, this supplement was awarded a **Generally Recognized as Safe Status (see appendix 1)** in the for a dose of up to 5 g. Similar doses of the emulsion from of the fish oil supplement are also being used in an ongoing clinical study in the USA (ClinicalTrials.gov Identifier: NCT02719665) measuring different outcomes to those being investigated in the present study.

5.6 Fish oil supplement manufacture

The fish oil and placebo will be provided by Metagenics and will be manufactured as detailed below:

Fish oils are manufactured following current Good Manufacturing Practice (cGMP), using semi-refined fish oil (anchovy/sardine oil) or pre-concentrated omega-3 fatty acid ethyl ester as a starting material. When semi-refined fish oil is used, the first step in the process is chemical esterification followed by a distillation step, in order to meet the same specifications as is the case for the pre-concentrated omega-3 fatty acid ethyl ester starting material. Concentration steps follow which are dependent on the degree of concentration of the starting material (natural heterogeneous material). The intermediates generated in the process are processed using carbon dioxide (CO_2) in a supercritical fluid extraction processes (SFE). The process benefits from the fact that CO_2 in supercritical conditions can operate at moderate temperatures without stressing the products and avoids further degradation of the products due to the inert properties in front of oxidation. A bleaching unit and or a deodorization step can be included if applicable. A bleaching step is usually performed to control and reduce oxidative parameters in oils, and to reduce the colour. A deodorization step is performed to reduce volatile components of the product and consequently its odour. The last step is homogenization with an added quantity of natural antioxidants such as a mixture of tocopherols, in order to improve the oxidative stability of the final product. The product is then packaged in a clean room into steel drums with an appropriate internal coating.

Reagents/processing aids are suitable for use in the production of the fish oil supplement. They are commonly used in food ingredient manufacturing processes as described in the table below.

Reagents/Processing Aids		
Reagent/Processing Aid	CAS Number(s)	21 CFR/GRN Citation(s)
Ethanol, food grade	64-17-5	184.1293
Sodium ethylate	141-52-6	NA*
Carbon dioxide	124-38-9	184.1240
Diatomaceous earth	NA	GRN No. 87; SCOGS No. 61
Nitrogen	7727-37-9	184.1540
Mixed natural tocopherols	59-02-9; 16698-35-4; 54-28-4; 119-13-1	182.3890; 184.1890

*Basic catalyst employed for esterification purposes; employed in food and pharmaceutical manufacturing processes.

The Specifications for the fish oil supplement (monohydroxylated ethyl ester of omega-3) are presented below in the table below.

Specifications for Fish Oil Supplement

Parameter (Assay Method)	Specification
General Characteristics	
Appearance (Visual)	Slightly yellow
Odour	Slight fish odor
Solubility	Almost insoluble in water. Miscible with acetone, ethanol, heptane, and methanol
Acid value (mg KOH/g) (Eur.Ph 2.5.1)	Max. 3
Peroxide index (meq O₂/kg) (Eur.Ph 2.5.5)	Max. 10

Fatty Acid Profile

EPA (mg/g, as FFA) (Eur.Ph 2.4.29)	100 – 260
DHA (mg/g, as FFA) (Eur.Ph 2.4.29)	300 – 450
Total omega-3 (mg/g, as FFA)* (Eur.Ph 2.4.29)	600 – 850

Heavy Metals

Lead (mg/kg) (AOCS Ca18c-91)	Max. 0.1
Arsenic (mg/kg) (AOAC 986.15)	Max. 0.1
Cadmium (mg/kg) (AOCS Ca18d-01)	Max. 0.1
Mercury (mg/kg) (AOAC 971.21)	Max. 0.1

Potential Contaminants

Copper (mg/kg) (AOCS Ca18-79)	Not specified, but analysis required
Iron (mg/kg) (AOCS Ca18-79)	Not specified, but analysis required
Cesium 134 (Bq/kg) (Gamma SPECTR)	Max. 3
Cesium 137 (Bq/kg) (Gamma SPECTR)	Max. 3
Iodine 131 (Bq/kg) (Gamma SPECTR)	Max. 3
Dioxins and Furans (pg WHO-TEQ/g) (EPA 1613)	Max. 1.75
Dioxin-like PCBs (pg WHO-TEQ/g) (EPA 1668)	Max. 3
Sum of dioxins and furans + dioxin-like PCBs (pg WHO-TEQ/g) (EPA 1613 and EPA 1668)	Max. 3
PCBs (209 congeners) (mg/g) (EPA 8082)	Max. 0.09
PAH (16 compounds) (GC/MS)	Not specified, but analysis required

* Sum of 18:3ω3, 18:4ω3, 20:4ω3, 20:5ω3, 21:5ω3, 22:5ω3, and 22:6ω3.

The fish oil product meets the above analytical specifications. Stability testing of fish oil supplement has been conducted at 25°C for up to 18 months. After a 18-month storage period, fish oil supplement was found to be stable in terms of peroxide value, acid value, total omega-3, EPA and DHA.

6. TRIAL OBJECTIVES

6.1 Aim of research

The aim of this research is to investigate whether fish oil supplementation increases the peripheral blood levels of SPM and whether fish oil supplementation also regulates peripheral white blood cell responses (including neutrophils, monocytes and platelets) to inflammatory stimuli.

6.2 Original hypothesis

Given that fish oils are rich in omega-3 essential fatty acids that are precursors in the biosynthesis of SPM **the hypothesis underlying the present study is: Fish oil supplementation increase peripheral blood levels of SPM precursors that may**

be converted to bioactive mediators which in turn will regulate white blood cell responses.

6.3 Primary Endpoint

The Primary endpoint of the study will be an increase in peripheral blood SPM levels that will be measured using established liquid chromatography tandem mass spectrometry based approach (see ref 17 above).

6.4 Secondary Endpoints

The secondary endpoints of this study are

- 1) an increase in *ex vivo* phagocytosis of *Escherichia coli* by peripheral white blood cells
- 2) a decrease in white blood cell activation when cells are incubated with an inflammatory stimulus (e.g. Platelet activation factor). This will be achieved by assessing the expression of adhesion molecules on peripheral blood cells using flow cytometry and fluorescently conjugated antibodies.

7. METHODOLOGY

7.1 Subject Selection

This is a single centre trial and Participants will be enrolled via adverts posted at each of the three QMUL campuses and on social media. No one with direct connections to the management or supervision of this study or any their collaborators will be eligible for recruitment. For QMUL student recruitment, permission from the Deanery will also be sought.

7.2 Inclusion Criteria

For participants to be included in the study they will need to meet the following criteria:

- 1) Able to provide informed consent
- 2) Men and women between the age of 18 and 45
- 3) Declare not to be taking aspirin, other NSAIDS, other form of medication or omega-3 fatty acid supplements for more than 2 weeks prior to screening and the duration of the participation.
- 4) Willingness to abstain from eating fish for 2 days before each study visit
- 5) Willingness to abstain from alcohol consumption for at least 24h prior to each study visit
- 6) Willingness to abstain from caffeine as directed before and during study

7.3 Exclusion Criteria

- 1) History of, chronic disorders, cardiovascular disease (e.g., heart disease, stroke), cancer, or diabetes or significant genetically inherited conditions.
- 2) Pregnancy or breast-feeding.
- 3) Hypothyroidism in the opinion of the investigator.
- 4) Liver disease in the opinion of the investigator.

- 5) Any abnormality or pre-existing disease which, in the opinion of the investigator, might either expose the subject to risk, or influence the validity of the results.
- 6) Women of childbearing potential not taking adequate methods of contraception
- 7) Inability to read and write in English
- 8) Participation in a clinical study of a new chemical entity, biological product or a prescription medicine, or loss of more than 400 mL blood, within the previous 3 months
- 9) Smoking
- 10) Presence or history of drug or alcohol abuse or intake of more than the amount of alcohol in the current guidelines on alcohol consumption

7.4 Study Design / Plan – Study Visits

This is an open label double-blind, placebo controlled, crossover study that aims to determine the dose of omega-3 fatty acids that leads to an increase in peripheral blood SPM levels and the kinetics of this regulation.

- Each participant will give a baseline blood sample then they will be given one of the randomly allocated three doses of fish oil supplement, or a matching placebo in one of 8 study groups [this will be on a 1:1:1:1:1:1:1:1 ratio]. Blood will be collected again at 2h, 4h, 6h and 24h after supplementation/placebo.

- This design allows to compare the levels of SPM pre and post supplementation and therefore to account for inter participant variation in circulating SPM levels as well as for any differences in white blood cell responses *ex vivo*.

- Using a crossover design and a placebo, diurnal variation in the levels of SPM (currently not known) will be checked. In addition, using each volunteer as their own control for comparison with each dose of supplement will further improve the power of the study.

- Each participant is expected to be involved in the study for a maximum of 11 weeks from initial consent and screening.

- Participants will be asked to refrain from consuming caffeine containing drinks at least 2h prior to their visit.

- Participants will be expected to refrain from alcohol intake for at least 24h before screening for the study, and for at least 24h before each cycle of the study.

- Participants will also be asked not to take other supplements, medications for the duration of the study, and to avoid fish containing meals for 2 days before each study cycle.

- For each cycle, the participants will make two visits, the first visit will be of a maximum of 8hrs. Here baseline (0hrs) blood sample will be obtained and the supplement/placebo given.

- Blood will be collected 2hrs, 4hrs and 6hrs following supplement/placebo intake and the participant will be free to leave after the 6hrs blood collection.

- During this time participants will be asked to refrain from drinking caffeine containing drinks such as coffee or tea.

- Participants will then be asked to return the next day (24h after fish oil supplement/placebo intake).

[figure not shown]
- The 24h blood draw should take a maximum of 30 min.

- After a minimum of 48 hours, and not more than two weeks participants will be asked to return, their eligibility criteria re-assessed and then administered the next supplement/placebo dose in the cycle as determined by the group they were assigned to at the beginning of the study (see Section 13.5.1)

- A first follow-up phone-call to the volunteer will be made to check well-being at 2 weeks (+/- 1 week) after the end of the volunteers last cycle
 - A Second follow-up phone-call to the volunteer will be made to check well-being at 4 weeks (+/- 1 week) after the end of the volunteers last cycle
 - If any adverse effects are reported by the volunteer they will be asked return for further evaluation.

The fish oil supplements that will be used in the present studies are isolated from Peruvian anchovies. These are then packaged as emulsions and supplied by Metagenics with whom we will have contractual agreement in place before the start of the study. Metagenics will also supply the emulsion that does not contain fish oil supplements to be used as placebo. Both of these products are not considered to be drugs or medicines and classified as foodstuffs.

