8.8 Clinical Protocol

At least 24h prior to consent, participants will be provided an information sheet by an appropriate method including email, post or by attending the clinic, detailing the rationale and hypothesis of the study and on attending the screening visit the study physician will address any questions that the participants may have. They will be asked to sign the informed consent and then their eligibility criteria will be assessed based on the inclusion criteria set out for the study. Basic observations, blood pressure, pulse, resting supine ECG, Blood samples for full blood count, biochemistry and glucose and CRP, then a physical examination will be performed.

Volunteers passing screening will then:

- Will give a baseline blood sample (12ml)
- Be given one of the randomly allocated three doses of fish oil supplement, or a matching placebo [this will be on a 1:1:1:1 ratio].
- Give blood (12ml/time interval) will be collected again at 2h, 4h, 6h
- Be allowed to leave and they will be asked to return the following day for the collection of the 24h blood sample.
- Be asked to return after a minimum of 48h but no later than 2 weeks
- Identity will be verified
- Blood will be obtained (12ml)
- Be given the next supplement dose/placebo that is listed on their assigned study group and the injection witnessed by a member of the study team.
- Blood will be obtained after 2h, 4h and 6h.
- Be free to leave and will be asked to return after 23h from supplementation
- The 24h blood sample will be collected and the participants will be asked to return again after a minimum of 48h and no later than 2 weeks for their next supplement dose/placebo cycle
- Identity will be verified
- Blood will be collected (12ml)
- Supplement/placebo will be administered and ingestion witnessed.
- Blood will be collected at the same intervals outlined above
- Participants will be asked to return for the last supplement dose/placebo listed on their study group at least 48h after the last blood donation (24h blood sample) but no later than 2 weeks.
- Essentially the same protocol outlined above will be followed for the last cycle.
- A first follow-up phone-call to the volunteer will be made to check well-being at 2 weeks (+/- 1 week) after the end of the volunteers last cycle
- A Second follow-up phone-call to the volunteer will be made to check well-being at 4 weeks (+/- 1 week) after the end of the volunteers last cycle

Participants can withdraw from the study at any time.

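### Dosing clock time and food are not required to match across a participant's four cycles, although section 7.4 uses the placebo cycle as the diurnal check

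*Combined protocol and SAP*

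**What the plan says.** Section 7.4 gives the placebo cycle a specific purpose: "Using a crossover design and a placebo, diurnal variation in the levels of SPM (currently not known) will be checked". The same bullet says that using volunteers as their own controls will improve power.

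All timing is relative to intake: "Blood will be collected again at 2h, 4h, 6h and 24h after supplementation/placebo". The length of the dosing day is capped but its start is not fixed: "For each cycle, the participants will make two visits, the first visit will be of a maximum of 8hrs". Cycles are spaced in days only; section 8.8 has "Be asked to return after a minimum of 48h but no later than 2 weeks".

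Some intake is controlled. Participants must "avoid fish containing meals for 2 days before each study cycle". On caffeine, 7.4 has "Participants will be asked to refrain from consuming caffeine containing drinks at least 2h prior to their visit" and, for the stay itself, "During this time participants will be asked to refrain from drinking caffeine containing drinks such as coffee or tea". Alcohol is barred for 24 h beforehand (7.2, 7.4). Section 8.11 makes medication, alcohol, other supplements or oily fish before the 24 h draw a ground for withdrawal.

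None of 7.4, 8.8 or the 8.9 schedule mentions time of day, fasting or ordinary meals.

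Section 9.4 tests the 2 h and 4 h values against the same person's pre-dose value with a Wilcoxon signed rank test. It contains no contrast with placebo and no diurnal analysis. Section 9.3 will carry forward to future trials the dose and time point with the greatest change.

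**The concern.** A placebo cycle shows what a dose cycle would have looked like without supplement only to the extent that the two were run under the same conditions. The article is an oil and the endpoint is a set of plasma lipid mediators, so both time of day and a meal could plausibly move the endpoint within hours. The plan controls caffeine, alcohol and fish, so its authors treated intake as a possible disturbance, but ordinary meals are left open.

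Two things are at stake. First, food taken between 0 and 4 h falls inside the window that 9.4 analyses and becomes part of the change score. Second, differences in start time or feeding between a person's cycles add variation to exactly the comparisons that the crossover is meant to sharpen: dose against dose, and dose against placebo. The choice of dose and time point in 9.3 depends on those comparisons. If clock times and meals are not recorded, they cannot be recovered later.

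**Working it through.** **1. Is the gap real?** Every timing rule in 7.4, 8.8 and 8.9 is either hours from intake or days between cycles. The 8 h cap with sampling to 6 h narrows the possible start times but does not fix them. Fish, alcohol, caffeine, supplements and medication are covered; other food is not.

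**2. Does the mismatch bias an active-versus-placebo contrast?** From the table in 8.3 (P = placebo; 1, 2, 3 = number of supplement capsules), groups 1 to 8 receive:

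- Cycle 1: P, 1, 2, 3, 3, 2, 1, P
- Cycle 2: 1, 2, 3, P, 2, 1, P, 3
- Cycle 3: 2, 3, P, 1, 1, P, 3, 2
- Cycle 4: 3, P, 1, 2, P, 3, 2, 1

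Each treatment appears twice in every cycle. A trend over cycles, such as later starts once volunteers know the routine, falls equally on all treatments. With random, blinded allocation, what remains is noise.

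**3. Size of the effect on the tests (assumed values).** The plan's N of 33 was reproduced first. Threefold odds give p = 3/(1+3) = 0.75. Noether's signed-rank formula, (z_alpha + z_beta)²/[3(p − 0.5)²], gives 32.97, hence 33, for a one-sided 5% test with 80% power. The two-sided value is 41.86, hence 42. The plan does not state sidedness, and the present point does not depend on it.

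The simulation used n = 33, a two-sided 5% Wilcoxon test and 2,000 runs. Units are the SD of the within-person change. *Drift* is a 0–4 h shift common to all cycles. *Added SD* is the extra per-cycle variation from unmatched clock time and food.

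Rejection with no supplement effect:

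| Drift | Added SD | Pre-post test (as in 9.4) | Active minus placebo |
|---|---|---|---|
| 0 | 0 | 4.2% | 4.5% |
| 0.25 | 0 | 28.9% | 5.0% |
| 0.5 | 0 | 77.6% | 5.4% |
| 0.5 | 1 | 49.7% | 5.5% |

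Over all nine settings run, the active-minus-placebo rate stayed between 4.1% and 5.5%.

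For power of the active-minus-placebo test, the true shift was set at z(0.75) = 0.674, and the SD of the difference is √[2(1 + added SD²)]:

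- Added SD 0: 0.674/1.414 = 0.48; power 73.8%
- Added SD 0.5: 0.674/1.581 = 0.43; power 64.2%
- Added SD 1: 0.674/2 = 0.34; power 45.0%

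**4. Clock time alone (assumed worst case, and only for a placebo-subtracted analysis).** Take a 24 h sinusoid of amplitude A, with w = 2π/24. If the two cycles start s hours apart, the largest residual in the change to t hours, over all phases, is 4A·sin(wt/2)·sin(ws/2).

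- s = 2 h: t = 4 h, 4(0.5)(0.2588)A = 0.52A; t = 2 h, 4(0.2588)(0.2588)A = 0.27A
- s = 3 h: t = 4 h, 4(0.5)(0.3827)A = 0.77A; t = 2 h, 4(0.2588)(0.3827)A = 0.40A
- s = 0: zero

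Without subtraction, as in 9.4, the largest drift is 2A·sin(wt/2): 1.0A at 4 h and 0.52A at 2 h. Equal start times do not change those two figures. A is unknown, as 7.4 itself says of diurnal variation. The documents give nothing from which to size a meal effect.

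**The case against.** The strongest reply is that silence is not evidence of variation. The figure in 7.4 and the diagram in 7.5 are not shown in the text reviewed, the participant information sheet is a separate document, and a site with an 8 h visit limit may well start everyone in the morning. That stands: the supportable statement is that constancy is not required, not that conditions differ.

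A reader might infer that uneven start times or meals bias the comparison with placebo. The 8.3 table does not support this. Treatments are balanced by period and allocation is random and blinded, so the cost is precision.

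A reader might also infer that holding conditions constant would let the placebo cycle isolate diurnal or meal effects. Section 7.4 promises only a check on diurnal variation, and with clock time and food both fixed the two effects would remain confounded with each other. Matching provides a better control for their combined effect.

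It is also fair to say that the sinusoid figures are worst-phase values (the root-mean-square is about 0.71 of each, for example 0.37A in place of 0.52A) for a subtraction that 9.4 never performs. Each cycle's 24 h sample also falls at the clock time of its own baseline, which gives a partial check, though not on the 2 h and 4 h values that are tested. Finally, the synopsis calls the study exploratory.

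These replies narrow the point but do not remove it. Balance by period does not stop food eaten between 0 and 4 h from entering the 9.4 change scores, and it does not restore the precision lost between cycles.

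**Conclusion.** The point holds as a cheap improvement. The plan uses the placebo cycle as its diurnal check and each volunteer as own control, but does not require a participant's cycles to match in dosing clock time, feeding state or food during the visit.

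There are two consequences. Food in the 0–4 h window can enter the pre-post tests, where a shared drift of 0.25 or 0.5 SD from any source would raise false rejection from about 4% to 29% or 78%. Unmatched conditions also cost precision: power of an active-minus-placebo contrast falls from about 74% to 64% or 45% for an added SD of 0.5 or 1. These figures rest on assumed normal changes and assumed drift and noise; the documents give no values for either.

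Matching alone would not remove diurnal drift from the 9.4 test. While 9.4 has no placebo contrast, the stated diurnal check has no analysis behind it.

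**What to change.** Add to 7.4 and 8.8:

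- Each participant starts all four cycles at about the same clock time and in the same fed or fasted state. The sponsor chooses the time, the state and the tolerance.
- Food during the visit is the same in content and timing in every cycle, and is kept out of the 0–4 h window where feasible. A meal after the 4 h draw would affect the 6 h sample, but equally in all cycles.
- Clock times of dose, draws and food are recorded in the CRF, with matching rows in the 8.9 schedule.

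Add to 9.4 a within-person comparison of the change from baseline on each dose with that person's placebo change at the same time point. The two parts complement each other: the contrast removes average drift, and matching restores precision.

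The cost is less flexibility in booking and a standard meal at visits that already last up to 8 h. The contrast needs no extra samples. The conduct rules must be in place before the first cycle.

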4. SUMMARY/SYNOPSIS

Short Title	SPM regulation by Fish Oil Supplements in Healthy Volunteers
Methodology	A randomised, double-blind, placebo-controlled study to determine whether fish oil supplementation regulates peripheral levels of specialized pro-resolving mediators and white blood cell responses in healthy volunteers
Research Sites	Barts and The London School of Medicine Queen Mary University of London William Harvey Research Institute [name]
Objectives/Aims	The objective of this study is to learn more about the biology of fish oil supplementation in human healthy volunteers by assessing the actions of these supplements in healthy volunteers.
Number of Participants/Patients	40
Main Inclusion Criteria	Able to provide informed consent, willingness to abstain from fish for 2 days before each study visit, physical examination, laboratory tests.
Statistical Methodology and Analysis (if applicable)	The results will be tabulated and assessed for biological activity of the fish oil supplement and any relationship between dose and primary variables. Because the study is exploratory in nature, there will be no formal statistical analysis of the data.
Proposed Start Date	July 2016
Proposed End Date	April 2016
Study Duration	9 months

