8.11 Subject Withdrawal

PI may/must withdraw participants from the study if during any point they intake any medication, alcohol, other supplements or oily fish prior to the last blood draw (24h). If participants are not able to make their next visit within the stipulate window (2 weeks + 48h from the supplement/placebo dose) they will be re-screened prior to re-enrolling.

If blood cannot be obtained at the 0h, 2h, 4h or 6h time intervals then the participant will be withdrawn from the primary analysis. If the blood cannot be withdrawn at the 24h interval the participant can still be included for primary and secondary endpoint analysis.

If a participant is withdrawn from the study they may re-enroll in the study after being >14 days free of medication.

If the participant withdraws before the completion of the 4th visit and dosing of supplement/placebo the samples and information will be still be analysed, but the study analysis will be primarily by per-protocol (complete treatment cycles only), although all data will also be analysed for Intention-to-treat as a secondary analysis.

Withdrawn subjects may be replaced at the discretion of the investigator.

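### Section 7.4 limits fish and alcohol only up to the start of each cycle, whereas 7.2 limits them before each visit and 8.11 makes intake before the 24h draw a ground for withdrawal; the three need reconciling

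*Combined protocol and SAP*

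**What the plan says.** Four places in the protocol bear on fish and alcohol.

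- **Section 7.2 (Inclusion Criteria)** ties both limits to the visit: "Willingness to abstain from eating fish for 2 days before each study visit" and "Willingness to abstain from alcohol consumption for at least 24h prior to each study visit". The synopsis does the same for fish: "willingness to abstain from fish for 2 days before each study visit".
- **Section 7.4 (Study Visits)**, which sets out what participants will be asked to do, ties both to the cycle. For fish they are asked "to avoid fish containing meals for 2 days before each study cycle". For alcohol they are to "refrain from alcohol intake for at least 24h before screening for the study, and for at least 24h before each cycle of the study".
- **Section 7.4** also says "For each cycle, the participants will make two visits": the dosing day, which the participant may leave after the 6h draw, and a return for the 24h draw. The schedule in 8.9 lists that return as a visit of its own.
- **Section 8.11 (Subject Withdrawal)** says the PI may/must withdraw participants if at any point "they intake any medication, alcohol, other supplements or oily fish prior to the last blood draw (24h". It gives no start to this period, and of fish it names only the oily kind.

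Section 7.4 does restrict some things after dosing: caffeine during the dosing visit, and other supplements and medications for the whole study. It says nothing about fish or alcohol between dosing and the 24h draw. Section 8.8, which goes through the cycles step by step, adds no dietary instruction.

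**The concern.** Visit and cycle are not interchangeable here, because a cycle contains two visits. Under 7.2 the second visit carries the restriction through to the 24h draw. Under 7.4 the restriction stops when the cycle starts.

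Two things are at stake.

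1. **Interpretation of the 24h sample.** Section 7.4 states an interest in the kinetics of the SPM response and uses the placebo cycle to check diurnal variation. Fish supplies the same kind of substrate as the test product. The protocol's own background (5.3, 5.5) reports a mild but significant rise in plasma SPM after 1 g of essential fatty acids, given with aspirin, as early as 4 hours after intake. A fish meal on the evening after dosing could therefore contribute to a 24h value, including one in a placebo cycle. The schedule in 8.9 has no diet or alcohol check, and its medication row is not marked at the 24h visits, so such intake might go unrecorded.
2. **Fair treatment of a compliant participant.** Someone who does exactly what 7.4 asks could drink, or eat oily fish, that evening and then meet the withdrawal condition in 8.11.

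**Working it through.** The plan gives no figure to reproduce on this point. The check is to put the restriction windows on one clock, with dosing at 0h.

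**Inputs**
- Visits in a cycle: 0h and 24h (7.4, 8.9).
- Lead time h: 48 hours for fish (2 days) and 24 hours for alcohol (7.2, 7.4).
- Participant may leave: after the 6h draw (7.4).
- Cycles per participant: 4 (8.3). Participants: 40 (synopsis, 8.3).

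**Formulas**
- 7.2 window = [0 − h, 0] together with [24 − h, 24].
- 7.4 window = [0 − h, 0].
- Gap = the part of the 7.2 window that the 7.4 window does not cover.

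| | 7.2 (per visit) | 7.4 (per cycle) | Gap |
|---|---|---|---|
| Fish, h = 48 | [−48, 0] and [−24, 24], so −48h to +24h | −48h to 0h | 0h to +24h, 24 hours |
| Alcohol, h = 24 | [−24, 0] and [0, 24], so −24h to +24h | −24h to 0h | 0h to +24h, 24 hours |

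The off-site part of the gap is 24 − 6 = 18 hours per cycle. It occurs in all four cycles, so it precedes 40 × 4 = 160 planned 24h samples. That is the number of samples to which the ambiguity applies, not an estimate of how many would be affected.

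**Which samples can the gap reach?**
- The 0h, 2h, 4h and 6h samples are drawn before the participant leaves. Anything eaten or drunk off site afterwards cannot alter them.
- Sections 9.3 and 9.4 name 2h and 4h against the pre-dose value for the planned Wilcoxon tests. They do not name 24h.
- The next cycle's baseline has its own preceding restriction under both 7.2 and 7.4.
- This leaves the 24h sample of the same cycle.

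**What does 8.11 add?**
- Its period also ends at the 24h draw, so on the end point it agrees with 7.2. Section 7.4 is the outlier.
- It differs from both sections in the term used for fish: non-oily fish is restricted before the visit or cycle but is not named as a withdrawal ground.
- A participant withdrawn after one cycle does not contribute later cycles to the primary analysis, which is per-protocol on complete treatment cycles.

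**The case against.** The strongest reply is that a protocol is read as a whole. Section 7.4 is silent about the evening after dosing; it does not give permission. Section 7.2 already asks for abstention before every visit, 8.11 treats intake before the 24h draw as a breach, and eligibility is re-assessed before each later dose. On this view the rule is in place and 7.4 is merely loosely worded. The Participant Information Sheet is a stand-alone document not available here, so what participants will be told cannot be established.

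Much of this stands. A reader might infer that there are three incompatible windows, or that fish and alcohol are expressly allowed after dosing. The documents support neither reading. A reader might also infer that the trial's main tests are contaminated. They are not, on the reasoning above, and 8.11 keeps a participant without a 24h sample in the primary and secondary endpoint analyses. Nor is loss of a participant automatic: the may/must wording leaves room for discretion, withdrawn participants may re-enrol or be replaced, samples already taken are still analysed, and all data enter a secondary intention-to-treat analysis.

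What does not stand is that the overall reading settles the matter. Section 7.2 is a criterion of willingness at entry, while 7.4 is the section that says what participants will be asked to do. No passage says which governs, and 8.11 attaches a consequence to the difference.

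**Conclusion.** The inconsistency is real and unresolved in the documents. Read alone, 7.4 leaves 24 hours per cycle, about 18 of them off site, without a fish or alcohol limit that 7.2 does impose and that 8.11 backs with possible withdrawal.

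Its reach is limited. The data at risk are the 24h kinetic values and the placebo diurnal check. The substrate argument applies to fish; for alcohol, the documents give no mechanism, and the issue is the conflicting instruction and the exposure to withdrawal. The loss of later cycles from the per-protocol analysis is possible but cushioned.

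The conclusion rests on two assumptions: that staff would instruct participants from 7.4, and that intake during the on-site hours up to 6h is controlled, since the protocol does not describe meals there. The documents give no rate of fish or alcohol intake on dosing evenings, so the number of affected samples or participants cannot be estimated from them.

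It should be corrected, because the correction costs little and the 24h samples are collected in every cycle.

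**What to change.** Reconcile 7.2, 7.4 and 8.11, and the matching participant instruction, so that they share:

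- one restriction window, stated in the same terms and covering whatever sampling period the trial intends to interpret;
- one term for fish, either all fish or oily fish;
- a withdrawal trigger that corresponds to what participants have been told, with the may/must wording settled.

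Which withdrawal rule applies is for the sponsor to decide; the point here is only that the sections must agree.

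The change is to wording. It needs no added visit, test or sample. Relative to 7.4 as it stands, participants would restrict their diet for at most one more evening per cycle; relative to 7.2, that evening is already covered.
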